5.5.8 Prohibited medication

Use of the treatments displayed in [Table 5-1](#) is NOT allowed after the start of the study treatment administration (Visit 101). If a prohibited medication is taken between start of study treatment administration and end of the treatment epoch, study drug must be discontinued. If taken during the follow-up epoch, the prohibited medication should be stopped as soon as possible. Use of the prohibited medication should be documented in the appropriate section of the CRF.

Some diuretics can enhance aminoglycoside toxicity by altering antibiotic concentrations in serum and tissue. TIP should not be administered concomitantly with ethacrynic acid, furosemide, urea, or intravenous mannitol.

Table 5-1 Prohibited medications requiring study drug discontinuation

Medication
Inhaled antibiotics except as per protocol
loop diuretics*
urea (intravenous)*
mannitol (intravenous)*
Cyclosporine
Tacrolimus
anti-TNF alpha
long-term treatment with corticosteroids >15mg/day (more than 28 days)
alpha 1 antitrypsine replacement therapy (Prolastin)
Methotrexate
Azathioprine
immune globulins (IV or subcutaneous)
anti-cytokines
Any other investigational treatments
Long-term oxygen therapy >15h per day

* Potential for nephrotoxicity

5.5.9 Emergency breaking of assigned treatment code

Emergency code breaks must only be undertaken when it is required to in order to treat the patient safely. Most often, study treatment discontinuation and knowledge of the possible treatment assignments are sufficient to treat a study patient who presents with an emergency condition. Emergency treatment code breaks are performed using the IRT. When the investigator contacts the system to break a treatment code for a patient, he/she must provide the requested patient identifying information and confirm the necessity to break the treatment code for the patient. The investigator will then receive details of the investigational drug treatment for the specified patient and a fax or email confirming this information. The system will automatically inform the Novartis (or CRO) monitor for the site and the Study Team that the code has been broken.

It is the investigator's responsibility to ensure that there is a dependable procedure in place to allow access to the IRT at any time in case of emergency. The investigator will provide:

- protocol number
- study drug name (if available)
- patient number

In addition, oral and written information to the subject must be provided on how to contact his/her backup in cases of emergency, or when he/she is unavailable, to ensure that unblinding can be performed at any time.

Study drug must be discontinued after emergency unblinding. Study drug must also be discontinued for any patient whose treatment code has been inadvertently broken.

5.6 Study Completion and Discontinuation

5.6.1 Study completion and post-study treatment

A patient will be considered to have completed the study when the patient has completed the last visit planned in the protocol. Completion of the study will be when the last patient has completed Visit 202.

Continuing care should be provided by investigator and/or referring physician based on patient availability for follow-up. This care may include resuming of their standard of care treatment as deemed by their physician.

5.6.2 Discontinuation of Study Treatment

Discontinuation of study treatment for a patient occurs when study drug is stopped earlier than the protocol planned duration, and can be initiated by either the patient or the investigator.

The investigator must discontinue study treatment for a given patient if, on balance, he/she believes that continuation would negatively impact the risk/benefit of trial participation.

Study treatment **must** be discontinued under the following circumstances:

- Patient wish
- Non-compliance of the patient with study procedures or investigator instructions, as per the investigator's judgment

- Emergence of AEs when worsened from baseline (Visit 2) or any newly occurring development of AEs with regards to the following:
 - If a patient is found to have a 20-dB or greater decrease in auditory acuity at one or more frequencies in 1 or both ears due to sensorineural deficit, the patient will be withdrawn from treatment and monitored until auditory acuity values return to the most recent pre-dose value (either at screening or baseline) or until study closure, whichever occurs first, i.e. the patient must be withdrawn from study treatment but should continue in the study. In case no pre-dose value is available for comparison, discontinuation of the study treatment and withdrawal of the patient from the study should be based on the investigator's best medical judgment.
- Any of the following laboratory abnormalities when worsened from baseline (Visit 101) or are a newly occurring AE:
 - Proteinuria $\geq 3+$, as confirmed according to Section 14, Appendix 2 Specific Renal Alert Criteria and Actions
 - Serum creatinine increase $\geq 50\%$ compared to baseline, as confirmed according to Section 14, Appendix 2 Specific Renal Alert Criteria and Actions
 - Estimated glomerular filtration rate (GFR) of ≤ 50 mL/min/1.73m²
- Pregnancy (see [Section 6.5.8](#) and [Section 7.6](#))
- Use of any of the prohibited medications detailed in [Table 5-1](#) and [Section 5.5.8](#).
- Any situation in which study participation might result in a safety risk to the patient.

Any renal finding needs to be followed up according to [Section 14 Appendix 2](#) Specific Renal Alert Criteria and Actions, which lists additional laboratory abnormalities that may require study treatment discontinuation based on clinical judgement. Confirmed renal events need to be followed up and documented according to [Section 14 Appendix 2](#).

Patients who interrupted study medication based on the investigator's decision should continue in the study, as per the visits and assessment schedule (see [Section 5.5.5](#)) - interruption of study treatment does not necessarily mandate withdrawal from the study.

Patients who discontinue study medication should NOT be considered withdrawn from the study. The patient should return to the clinic as soon as possible, after discontinuation of study drug, for a study treatment discontinuation visit and then enter the 2-month follow-up epoch. Treatment discontinuation visit assessments detailed in the "treatment discontinuation visit" (TD) in [Table 6-1](#) should be completed and recorded in the CRF. If they fail to return for these assessments for unknown reasons, every effort should be made to contact them as specified in [Section 5.6.4](#). The investigator must determine the primary reason for the patient's premature discontinuation of study treatment and record this information on the Dosage Administration CRF.

After study treatment discontinuation, at a minimum, in abbreviated visits, the following data should to be collected at clinic visits or via telephone visits:

- new / concomitant treatments
- adverse events/Serious Adverse Events

If the patient cannot or is unwilling to attend any visit(s), the site staff should maintain regular telephone contact with the patient, or with a person pre-designated by the patient. This telephone contact should preferably be done according to the study visit schedule.

The investigator must also contact the IRT to register the patient's discontinuation from study treatment.

If study drug discontinuation occurs because treatment code has been broken, please refer to [Section 5.5.9](#).

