5.6.5 Early study termination by the sponsor

The study can be terminated at any time for any reason by Novartis. Should this be necessary, the patient should be seen as soon as possible and treated for a prematurely withdrawn patient. The investigator may be informed of additional procedures to be followed in order to ensure that adequate consideration is given to the protection of the patient's interests. The investigator will be responsible for informing the Institutional Review Board/Independent Ethics Committee (IRBs/IECs) of the early termination of the trial.

6 Visit schedule and assessments

The study will consist of a screening epoch, a 112-day treatment epoch and a 56-day follow-up epoch after the last treatment.

[Table 6-1](#) lists all of the assessments and indicates with an “x” when the visits are performed. Patients/subjects must be seen for all visits on the designated day, or as close to it as possible. All data obtained for these assessments must be supported in the patients' source documentation. Visit 2 (baseline) and Visit 101 are performed on the same day (Day 1). Patients are required to complete specific ‘baseline assessments (Inclusion/Exclusion criteria) as part of Visit 2 prior to being randomized and moving into the treatment epoch (Visit 101). Missed or rescheduled visits should not lead to automatic discontinuation.

Patients/subjects who prematurely discontinue the study for any reason should be scheduled for a visit as soon as possible, at which time all of the assessments listed for the final visit will be performed. At this final visit, all dispensed investigational product should be reconciled and the adverse event and concomitant medications reconciled on the CRF.

At a minimum, patients will be contacted for safety evaluations during the 30 days following the last administration of study treatment.

The PRO questionnaires should always be completed before any other assessments at a study visit. **The following assessments should be performed prior to dosing for applicable visits:**

- Physical examination
- Vital signs
- Body weight
- Serum specimen for Safety Laboratory
- Serum pregnancy test
- Urine pregnancy test
- Urinalysis
- Sputum specimens (2 separate specimens) for central analysis
- Pre-dose serum specimen for PK sub-study (if applicable)
- Audiology at Visit 2
- Pre-dose spirometry

[REDACTED]

[REDACTED]

[REDACTED]

Table 6-1 Assessment schedule

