- **Placebo:** The reference product consists of placebo capsules. The dose regimen for the reference product is 4 capsules blinded, inhaled b.i.d. via the T-326 Inhaler, for 112 days (on treatment).

There will be 3 study epochs with a total of 9 visits ([Figure 1](#)):

- Screening: up to 28 days with 1 clinic visit
- Double-blind treatment (within cohort): 112 days with 6 clinic visits [Visit 101 (Day 1), Visit 102 (Day 8), Visit 103 (Day 29), Visit 104 (Day 57), Visit 105 (Day 85) and Visit 106 or study treatment discontinuation (TD) (Day 113)]
- Follow-up: 56 days with 2 clinic visits [Follow-up Visit 201 (Day 141) and Follow-up Visit 202 or premature subject/patient discontinuation (PSD) (Day 169)]

The total duration of the study is expected to be up to 196 days. Patients will be assessed for safety, tolerability and efficacy (see protocol [[Table 6-1 – Assessment schedule](#)]).

Figure 1 Study design

The primary efficacy endpoint is the absolute change from baseline to Day 29 of treatment in the bacterial load in sputum in log₁₀ colony forming units (CFUs) of *P. aeruginosa*. Baseline is defined as the last measurement prior to the first dose of blinded study drug.

No interim analysis for efficacy is planned. There is an independent data monitoring committee (DMC) assigned to monitor the safety during the study; further details are defined in the DMC Charter.

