2.1.1 General definitions

Study drug is defined as any single dose of TIP or placebo administered to the patient as part of the required study procedures.

The date of first dose of study drug is defined as the date of first administration of TIP or placebo; the date of last dose of study drug is defined as the date of the last administration of TIP or placebo.

For dates on or after the date of first dose of study drug, study day is defined as [date of interest – date of first dose of study drug] + 1. For dates before the date of first dose of study drug, study day is defined as [date of first study drug – date of interest].

For each visit, the date recorded by the investigators in the eCRF (variable SVSTDTC in the SDTM SV dataset) will be considered as the visit date in all the algorithms and the listings.

In general, the nominal visits will be used for the by visits summaries. However, for early treatment discontinued patients, data collected at end of treatment (EOT) visit will be mapped to next planned visits after their last scheduled visits before the discontinuation.

Baseline is defined as the last non-missing result prior to the first administration of study drug.

End/last date of study for each patient is defined by the date of last contact as recorded in the database.

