2.6 Analysis of secondary and exploratory efficacy objective(s)

For efficacy analysis, patients assigned to placebo arms will be pooled across the 3 cohorts, as the number of placebo capsules is not expected to impact the efficacy assessments. Unless otherwise specified, the following analysis will be conducted both over the treatment epoch (through Day 113) and over the entire study period (through Day 169).

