The primary efficacy parameter (CFU) will be analyzed using a similar ANCOVA model as used in primary efficacy analysis at Day 85, Day 113 and Day 169. The model will contain treatment, baseline CFU (in log₁₀ unit), and baseline macrolide use (yes/no).

The analysis will not be performed by the subgroup of morphotypes. Six pairwise comparisons will be evaluated as specified in [Section 2.6.3](#). The estimated adjusted treatment difference for each of the 6 comparisons (TIP–placebo) will be displayed along with the associated standard error, 2-sided 95% CI. In addition, CFU data will be summarized by morphotype and sum of all morphotypes at each scheduled visit.

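### Early stoppers' Visits 201/202 appear to fall well before Days 141/169, yet the SAP has no rule that keeps them from being analysed under those day labels

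*Protocol*

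**What the plan says.** **Path after stopping.** Protocol 5.6.2 says that patients who discontinue study drug are not withdrawn. They return as soon as possible "for a study treatment discontinuation visit and then enter the 2-month follow-up epoch". Protocol Section 6 describes "a 112-day treatment epoch and a 56-day follow-up epoch after the last treatment". Table 6-1 puts the TD visit in the same column as Visit 106, so the next scheduled visits are 201 and 202. Patients who only interrupt study drug are treated differently: they continue on the visit and assessment schedule.

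**Data after stopping.** Protocol 5.6.2 asks, as a minimum, for new and concomitant treatments and AEs/SAEs, by clinic or telephone, and gives no end day. For patients who cannot or will not attend, it adds: "This telephone contact should preferably be done according to the study visit schedule". Protocol 5.6.4 does not allow a patient to be called lost to follow-up before the scheduled end-of-study visit has passed.

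**Analysis.** SAP 1.1 fixes the follow-up visits on calendar days: "Follow-up: 56 days with 2 clinic visits [Follow-up Visit 201 (Day 141) and Follow-up Visit 202" (Day 169). SAP 2.1.1 states: "In general, the nominal visits will be used for the by visits summaries". The one exception for early stoppers is that "data collected at end of treatment (EOT) visit will be mapped to next planned visits after their last scheduled visits before the discontinuation". CFU is then analysed "using a similar ANCOVA model as used in primary efficacy analysis at Day 85, Day 113 and Day 169" (SAP 2.6.3.1). The QOL-B respiratory symptom model in SAP 2.10 has visit terms from 102 to 202. For the other secondary outcomes, the default in SAP 2.6 is that "the following analysis will be conducted both over the treatment epoch (through Day 113) and over the entire study period (through Day 169").

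**The concern.** Two things follow if these passages are taken together.

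1. A sputum sample or QOL-B score taken at an early stopper's Visit 202 carries the Day 169 label, although it may have been taken months before Day 169. The Day 169 CFU means and the Visit 201/202 terms of the QOL-B model then mix different times since randomization, in a proportion that depends on how many patients stop and when.
2. The proportions of patients with an exacerbation, anti-pseudomonal antibiotic use or hospitalization (SAP 2.6.1.2 to 2.6.1.4 and 2.6.3.2 to 2.6.3.4) are crude. If contact ends at an early Visit 202, an arm with more early stopping has fewer days in which to record an event, and its proportion tends to look lower for that reason alone.

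This matters because the FAS is said to follow the intent-to-treat principle, and because Protocol 3.2 expects tolerability to be driven mostly by the amount of powder inhaled. Stopping may therefore differ between cohorts.

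**Working it through.** **The plan's own days.** End of treatment is Day 113. Visit 201 = 113 + 28 = Day 141 and Visit 202 = 113 + 56 = Day 169, as Table 6-1 and SAP 1.1 state. Follow-up visits are thus defined by their distance from the end of treatment.

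**Early stoppers.** Let T be the study day of the TD visit, with follow-up counted from T.

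- Visit 201 = T + 28 and Visit 202 = T + 56.
- Days early = 169 − (T + 56) = 113 − T.
- Days between Visit 202 and Day 113 = max(0, 57 − T).

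| TD day T | Visit 201 | Visit 202 | Days early | Days short of Day 113 |
|---|---|---|---|---|
| 8 | 36 | 64 | 105 | 49 |
| 17 (stop Day 15, lag 2 days) | 45 | 73 | 96 | 40 |
| 29 | 57 | 85 | 84 | 28 |
| 57 | 85 | 113 | 56 | 0 |
| 62 (stop Day 60, lag 2 days) | 90 | 118 | 51 | 0 |
| 85 | 113 | 141 | 28 | 0 |

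The two-day lag is an assumption. Counting the 56 days from the last dose, as Section 6 words it, moves the two lagged rows two days earlier (Visit 202 on Days 71 and 116). As a share of 169 days, the time after Visit 202 is 96/169 = 57% for the Day 15 stop and 51/169 = 30% for the Day 60 stop. Visit 202 precedes Day 169 for every early stopper. It precedes Day 113 only when T is before Day 57.

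**How many patients.** Protocol 9.7 allows for about 20% discontinuation. That gives 0.20 × 180 = 36 of the planned patients, or 0.20 × 107 = 21 of those randomized when recruitment stopped (SAP Section 1). At the planned ratios an active arm holds 107 × 1/3 × 2/5 = 14 patients, so about 3 early stoppers. SAP 2.6.3 compares each of the six active arms separately with pooled placebo.

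**Follow-up time.** Assume stop days spread evenly over Days 1 to 112, no TD lag, and contact ending at Visit 202. The mean shift is then 56.5 days. With 36 stoppers, 36 × 56.5 = 2,034 of 180 × 168 = 30,240 person-days to Day 169 are lost, or 6.7%. The figure is 3.4% at 10% discontinuation and 10.1% at 30%. The percentages are the same for 107 patients.

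**Which analyses are exposed.**

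- Exposed to the label: the CFU ANCOVA at Day 169, and the Visit 201 and 202 terms of the QOL-B model. No CFU ANCOVA is planned at Day 141.
- Exposed to unequal follow-up: the crude proportions.
- Already protected: Cox models, which censor, and the study-period rate models for exacerbations and antibiotic use, which have log time in study as offset (SAP 2.6.3.2 and 2.6.3.3).
- Not involved: the Day 29 primary endpoint, so far as the 201/202 labels go.

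**The case against.** **Re-timing is an inference.** No sentence says TD + 28 or TD + 56, and Protocol Section 6 also asks that visits be held on the designated day. This stands as a reservation. But a two-month follow-up entered straight after the TD visit cannot end on Day 169 for someone who stops early, so the passages need reconciling on either reading. The nominal-visit sentence speaks of summaries, but the SAP offers no other assignment rule for the models.

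**Data may be collected for longer.** A reader might infer that outcomes through Days 113 and 169 are simply not observed in early stoppers. The documents do not support that. Event and treatment data are to be collected after stopping with no end day; exacerbations are recorded with the AEs and antibiotics with concomitant medication. Protocol 5.6.4 can be read as contact up to the scheduled end of study. Even with contact ending at Visit 202, Day 113 is reached by everyone whose TD visit is on Day 57 or later. For the Day 113 time-to-event analysis, the cut comes mainly from the SAP's censoring at last dose, not from the visit path.

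**Unequal follow-up is largely handled.** Kaplan-Meier analyses are already planned for exacerbation, for discontinuation due to exacerbation and for hospitalization, and the crude proportions are descriptive. This narrows the point to the proportions themselves and to antibiotic use, which has a Cox model but no Kaplan-Meier analysis.

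**Time off drug is a sensible axis.** Protocol 3.3 gives the follow-up the purpose of showing persistence of effect. Visits 28 and 56 days after stopping serve that purpose. This stands, and is a reason to keep those visits and summarise them on that axis. It does not justify a Day 169 label.

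**Direction of bias is not shown.** A reader might infer that the plan favours TIP. The documents give no stopping rates by arm, and the 2:2:1 allocation in each cohort balances powder load when pooled regimens are compared with pooled placebo. The direction depends on where stopping turns out to be more frequent.

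**Conclusion.** The point holds for labelling and for the crude proportions. On the natural reading of Protocol 5.6.2, Section 6 and Table 6-1, every early stopper's Visit 202 falls before Day 169, by 1 to 105 days for TD visits between Day 112 and Day 8. The SAP leaves such values under the Day 141/169 labels. At the 20% allowance this concerns about 21 of 107 patients. That allowance belongs to the sample-size calculation, so the count is illustrative, as is the 6.7% of person-days lost (3.4% to 10.1% for 10% to 30% discontinuation, evenly spread stops and no contact after Visit 202).

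The reach is limited. The primary endpoint is not affected by these labels, the sample size and power figures do not depend on them, most event models allow for shorter follow-up, and SAP Section 1 already says that inferential analyses can be considered exploratory. The change should be made because it is cheap and because a Day 169 estimate that mixes study days has no clear meaning. What the documents leave open is when data collection ends after the TD visit.

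**What to change.** 1. **SAP 2.1.1, 2.6.3.1 and 2.10.** For models labelled by day since randomization, assign early stoppers' follow-up CFU and QOL-B data to analysis visits by actual study day. Summarise Visits 201/202 separately by days since last dose, to describe persistence. Cost: one windowing rule, and fewer values at Day 169, so report the number contributing in each arm.
2. **SAP 2.6.3.2 to 2.6.3.4.** Report Kaplan-Meier cumulative incidence at Day 113 and Day 169, alongside or in place of the crude proportions, and add it for antibiotic use. For the Day 113 estimate, count events observed after the last dose instead of censoring there. Cost: a few extra tables from data already collected.
3. **Protocol 5.6.2, 5.6.4 and Section 6, with SAP 2.1.1.** Reconcile these passages on when Visits 201/202 take place after an early stop. State that the contacts Protocol 5.6.2 already allows for AEs, exacerbations, hospitalizations and concomitant antibiotics continue to Day 169 for patients still in the study, without removing the clinic visits that follow the TD visit. Cost: some extra telephone contacts per early stopper, and a longer period of contact for them. Where patients have already finished, only items 1 and 2 can be applied.

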5.6.3 Withdrawal of informed consent

Subjects may voluntarily withdraw consent to participate in the study for any reason at any time. Withdrawal of consent occurs only when a subject:

- Does not want to participate in the study any longer, and
- Does not allow further collection of personal data

In this situation, the investigator should make a reasonable effort (e.g. telephone, e-mail, letter) to understand the primary reason for the subject's decision to withdraw his/her consent and record this information.

Study treatment must be discontinued and no further assessments conducted, and the data that would have been collected at subsequent visits will be considered missing.

Further attempts to contact the subject are not allowed unless safety findings require communicating or follow-up.

All efforts should be made to complete the assessments prior to study withdrawal. A final evaluation at the time of the subject's study withdrawal should be made as detailed in assessment table ([Table 6-1](#).)

Novartis will continue to keep and use collected study information (including any data resulting from the analysis of a subject's samples until their time of withdrawal) according to applicable law.

All biological samples not yet analyzed at the time of withdrawal will no longer be used, unless permitted by applicable law. They will be stored according to applicable legal requirements.

The investigator must also contact the IRT to register the patient's withdrawal from the study.

Patients who prematurely discontinue study treatment or withdraw from the study will not be replaced.

